Health Promoters will invite members of their social networks to participate in the study. We will limit network participants to a maximum of 12 per HP for purposes of measurements and the mentorship/education portion of the intervention. Eligibility criteria include (1) self-identification as Hispanic or Somali, (2) member of a social network identified in the social network analysis, (3) age ≥ 18 , (4) willingness to participate in all aspects of the study; and (5) provision of informed consent. Exclusion criteria include (1) pregnancy at the time of enrollment and (2) serious medical conditions or disabilities that would make physical activity difficult. To avoid stigmatization, a normal weight (BMI <25) will not exclude individuals from participating in the intervention, but they will be excluded from the measurements and analyses. Based on our network analysis, we expect 81% of Hispanic and 50% of Somali participants screened to be overweight or obese. When an HP identifies an individual, they will accompany a language-congruent study assistant and study coordinator to their home or community location, where eligibility will be determined, and informed consent and baseline measures will be obtained. Based on our preliminary data, we will not restrict the participants to a particular age group for either population, as there was no significant clustering found by age. Likewise, network data, and community feedback, have helped to determine that we will not restrict Hispanic groups to gender concordance, but Somali groups will be gender-concordant, due primarily to cultural and religious beliefs and practices. Our social network data also indicate that 81% of Hispanic participants and 94% of Somali participants were immigrants born outside the US. The 19% of Hispanic and 6% of Somali immigrants born in the US were all first-generation immigrants (i.e., their parents were born outside the US). While this study targets foreign-born immigrant populations, US-born members of social networks will not be excluded.

Study Participants will receive four \$75 gift cards, one for each measurement time: baseline, 6 months measures, 12 months measures, and 24 months measures. The health promoters will receive up to \$100 for participating in training, \$600 for delivering the program during the first 6 months, and \$300 for delivering the program in the second 6 months.

Interventions

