Demographic, acculturation, and structural racism measures. The following demographic data will be collected at baseline: age, gender, ethnicity, country of birth, annual household income, education level, employment status, and use of social media. Participants will report on the following proxies for acculturation: years lived in the US, primary language spoken at home, and level of English language proficiency on a 5-point Likert scale.¹⁴⁴ Degree of dietary acculturation¹⁴⁵ will be assessed from results of 24-hour dietary recall described below. The following measures of structural racism will be obtained at baseline: Home address for automated collection of geolocation-based measures (Minnesota Measure of Structural Racism [MMSR], Area Deprivation Index [ADI], County Structural Racism Index); Everyday Racism Scale, Discrimination in Medical Settings Scale, and Medical Mistrust Scale.

Primary outcome measures.

BMI: Weight will be measured to the nearest 0.1 kg using a portable scale (Seca 880 Digital Floor Scale). Height will be measured to the nearest 0.1 cm at baseline only using a stadiometer. Participants will be asked to remove shoes prior to both measurements. BMI is calculated as weight (kg)/height squared (m²). Waist circumference will be measured to the nearest 0.1 cm at the narrowest part of the torso between the ribs and the iliac crest. Participants will remove excess clothing prior to the measurement and smooth the remaining clothing against the skin. Two measurements will be taken; if the difference between the two measures is more than 2.0 cm, a third measurement will be taken. The average of the two closest measures will be used.

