Social network sub-groups are sufficiently discrete for randomization: Our social network data analysis determined that these communities were composed of enough discrete sub-groups for randomization. An example of this is that the Hispanic network had 144 unique sub-groups. When considering only sub-groups composed of five or more individuals, there were still 88 sub-groups identified using modularity calculations. This is a sufficient number of sub-networks for randomization, especially when considering the approximately equal number of Somali networks. Therefore, the high clustering observed in our preliminary data, as demonstrated by the high modularity of the networks, indicates that there are clearly distinct subgroups in the networks and that randomization via subgroups is feasible and appropriate for the study.

Sample size considerations

Stepped wedge cluster randomization trials typically have more statistical power than other cluster randomized designs.¹¹⁵ This is because each cluster is able to serve as its own control, accounting directly for the within cluster correlation of outcomes. In addition, the impact of intra-cluster correlation on power is typically smaller than on conventional cluster randomized trials.¹⁷¹ For the current study, we expect each HP to recruit 6 to 8 participants, so assume 7 per cluster and a substantial loss to follow up of 20% over 12 months. We assume a conservative intra-cluster correlation in outcomes of 0.10 to calculate the design effect DE_{sw} based on the formula:^{115,171}

$$DE_{sw} = \frac{1 + \rho(ktn + bn - 1)}{1 + \rho \left(\frac{1}{2}km + bn - 1 \right)} \cdot \frac{3(1 - \rho)}{2t \left(k - \frac{1}{k} \right)}$$

where $k = 2$ is the number of steps (including baseline), $b = 1$ is the number of measurements per subject in the baseline step, $t = 1$ is the number of measurements per subject at each step, and $n=7$ is the number of subjects per cluster. Assuming 80% follow up and equal

distribution across clusters, and a 80% power, we estimate the detectable standardized effects (SDs) for a range of numbers of enrolled HPs with a maximum probability of a Type II error of 0.05.

SD	HPs	N total
0.1	478	1673
0.2	120	420

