0.3 53 187 For the primary endpoints, a third standard deviation (0.3SD) difference between groups will be considered clinically meaningful.¹⁷² On the basis of the previous Healthy Immigrant Families study, we will assume a 0.1 standard deviation change in the control group ("contamination") so this represents a 0.4SD change in the intervention group. Therefore, the study will accrue 54 clusters (27 per group) with approximately seven participants in each cluster, for a total sample size of approximately 378 network participants.

Data Analysis

All analyses will be appropriate for stepped wedge trials. In the direct effects model, the co-primary endpoints will be changes in BMI and waist circumference from baseline to month 12 and the 12-month change in the Ajzen TPB, the common outcome for C2DREAM. We will use mixed effects regression models to adjust for correlations within social network clusters and over time.¹¹⁴ Models will include indicators for intervention status, step, and their interaction. Covariates indicated above including demographics (e.g., sex, years since arrival to the US) and social covariates will be included in profile analysis models to assess the sensitivity of the primary analysis conditional on these potential concomitant (mediating) influences. All secondary endpoints will be analyzed using the same methods as used for the primary endpoints.

Missing data will be handled in several ways using an extensive library of macro procedures designed specifically for such tasks by the Mayo Clinic Division of Biostatistics.¹⁷³ Simple imputation methods such as minimum, average, or maximum values carried forward will be followed by multiple imputation methods to assess the robustness of the study results in the presence of the missing data. All models will be assessed for goodness of fit, with effects reported with confidence intervals. All hypothesis tests will use $\alpha = 0.05$ to determine significance.

Bibliography

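### Pregnancy is excluded only at enrolment and not recorded afterwards, so weight and waist measured in pregnancy would enter the co-primary 12-month changes in both arms as noise

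*Combined protocol and SAP*

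**What the plan says.** Under Participants, Recruitment, and Enrollment the plan states: "Exclusion criteria include (1) pregnancy at the time of enrollment and (2) serious medical conditions or disabilities that would make physical activity difficult". Adults of 18 and over are eligible, and on age it adds "we will not restrict the participants to a particular age group for either population". Women are expected in numbers: the network survey was 50% female and the pilot 60.5% female (Preliminary Data).

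Measurements are taken at baseline and at 6, 12 and 24 months, with month 12 as the primary time point. Under Primary outcome measures, "Height will be measured to the nearest 0.1 cm at baseline only using a stadiometer", and "Waist circumference will be measured to the nearest 0.1 cm at the narrowest part of the torso between the ribs and the iliac crest". Neither rule mentions pregnancy. The demographic, clinical, behavioural, theory-based and diffusion measures listed in the following paragraphs do not include pregnancy status at follow-up.

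In Data Analysis, "the co-primary endpoints will be changes in BMI and waist circumference from baseline to month 12" (with a 12-month theory-of-planned-behaviour measure alongside), analysed by mixed models. For missing data, "Simple imputation methods such as minimum, average, or maximum values carried forward will be followed by multiple imputation methods". Nothing there deals with a value measured in pregnancy.

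**The concern.** Because height is fixed at baseline, change in BMI is change in weight divided by a constant. Weight and waist in pregnancy, or shortly after birth, reflect more than adiposity, which is what these endpoints are meant to capture. By excluding pregnancy at baseline the plan accepts this for the first half of the change score but leaves the second half open. Women of childbearing age are eligible and follow-up lasts 24 months, so some pregnancies are foreseeable.

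At stake is precision in two co-primary endpoints. There is also a practical problem: if status is not recorded at the visit, an analyst cannot reliably recover it later, so even a sensitivity analysis would be out of reach.

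**Working it through.** The plan gives no figure on this point, and the documents contain no pregnancy rate, gestational gain or SD of 12-month change. What follows is therefore a break-even calculation, not a forecast.

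**Inputs from the plan**
- Size: "for a total sample size of approximately 378 network participants" (Sample size considerations). Specific Aims says approximately 480, so both are shown.
- Follow-up: "so assume 7 per cluster and a substantial loss to follow up of 20% over 12 months", hence 80% measured at month 12.
- Intra-cluster correlation 0.10; nominal power 80%; significance level 0.05 (taken as two-sided).

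The 80% is used only as a starting point. The 53 Health Promoters tabulated for 0.3 SD do not follow from the printed formula and inputs, but that is a separate matter and this point does not depend on it.

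**Assumptions**
- 1:1 allocation.
- SD of 12-month weight change 5 kg.
- Pregnancy adds g = 8 kg at measurement (range 4 to 12 kg), independently of the rest of the change.

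**Step 1: numbers measured per arm**
- N = 378: 378 × 0.80 / 2 = 151.
- N = 480: 480 × 0.80 / 2 = 192.

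**Step 2: share pregnant that adds 10% to the variance**

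If a share p of participants gains an extra g, the variance of change rises by p(1 − p)g². Set p(1 − p)g² = 0.10 × SD² = 0.10 × 25 = 2.5.

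| Assumed gain g | p(1 − p) | p | Per arm, N = 378 | Per arm, N = 480 |
|---|---|---|---|---|
| 4 kg | 2.5/16 = 0.156 | 19.4% | 29 | 37 |
| 8 kg | 2.5/64 = 0.039 | 4.1% | 6 | 8 |
| 12 kg | 2.5/144 = 0.017 | 1.8% | 3 | 3 |

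At 378 there would be 151 × 0.50 = 76 to 151 × 0.605 = 91 women per arm, so 6.2 pregnancies is about 7% to 8% of the women. The share among women of childbearing age would be higher, because there is no upper age limit.

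**Step 3: effect on power**
- Inflating the whole variance by 1.10: Φ((1.96 + 0.84)/√1.10 − 1.96) = Φ(0.71) = 76%.
- Allowing for clustering, with 7 × 0.80 = 5.6 measured per cluster: the design effect is 1 + 4.6 × 0.10 = 1.46. If the extra 0.10 falls at the individual level, the ratio is (1.46 + 0.10)/1.46 = 1.068, giving Φ(2.80/√1.068 − 1.96) = Φ(0.75) = 77%. Pregnancies concentrated in women's groups would narrow the gap between the two figures.

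**Step 4: cost of setting the same values to missing**

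Losing 4.1% of values gives Φ(2.80 × √0.959 − 1.96) = Φ(0.78) = 78% without clustering. With clustering, 5.6 × 0.959 = 5.37 per cluster. The variance of a cluster mean goes from 1.46/5.6 = 0.261 to 1.437/5.37 = 0.268, and power is about 79%. At this break-even, dropping the values costs slightly less power than keeping them.

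**Waist**

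Pilot Table 2 shows a mean change of −1.7 cm, P = 0.14, n = 39. If that came from a paired t-test (the table names none), t = 1.507 and the SD of change is 1.7 × √39/1.507 = 7.0 cm over 12 weeks. With an assumed +15 cm in pregnancy, about 3 per arm at N = 378 would add 10% to the variance; with +5 cm about 41, and with +25 cm about 1. A larger SD over 12 months would raise these counts.

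**The case against.** The strongest reply is that the plan does have a default. A weight taken in pregnancy is an observed value, the endpoint is change to month 12, and the missing-data paragraph gives no licence to delete observations. Read literally, the value is analysed as measured, in the arm as randomised. That stands, and it rules out the stronger reading that the primary endpoint is undefined or that the plan permits two answers. It does not remove the point, because that default puts gestational weight into an adiposity endpoint.

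Other inferences a reader might draw are also not supported:
- **Bias between arms.** Pregnancies should balance in expectation, and randomisation is stratified by the Health Promoter's sex, which helps because Somali groups are single-sex. A chance imbalance is not a second harm. It is how the extra variance shows itself, and the confidence interval already carries it.
- **Change pushed upward in every case.** An early pregnancy may add little or no weight.
- **The same damage to Life's Simple 7.** Its weight item is scored in three BMI bands. A woman already at 30 or above scores 0 and cannot fall further; others change only if they cross a cut-point.
- **Carry-forward making matters worse.** An analyst who set pregnancy values to missing would set the month-6 value to missing too, so it could not be carried into month 12.

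It is also fair to say that the size rests on assumptions, and that setting values to missing because of a post-randomisation event replaces observed data with modelled data. Both are accepted below.

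**Conclusion.** The point holds as a cheap improvement, not as a threat to validity. Pregnancy is checked once, is not recorded again, and the analysis as written treats month-12 weight and waist in pregnancy as ordinary change in both arms. The consequence is added noise in BMI and waist change.

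With an assumed 8 kg gain and SD of 5 kg, about 6 pregnant women per arm at 378 participants, or about 8 at 480, cost roughly 3 to 4 points of power from a nominal 80%. Across gains of 4 to 12 kg the count runs from 29 down to 3 per arm at 378. Whether any of these counts would be reached cannot be judged from the documents, and the effect could be negligible if pregnancies are few or early.

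**What to change.** 1. At months 6, 12 and 24, the existing blinded measurement team asks privately whether the participant is pregnant or has given birth within a set window (for example 6 months), and records the answer. No arm information is needed. Because Health Promoters organise measurement times and places, ask away from them and from the group.
2. Before unblinding, add to Data Analysis that BMI and waist measured in pregnancy or in that window are set to missing in the primary model and not carried forward, and that the participant stays in her randomised arm through her other visits.
3. As sensitivity, repeat the analysis with all values as measured, and report the number of affected visits by arm.

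The cost is one question at up to three existing visits: at most 378 × 3 = 1,134 askings, or 480 × 3 = 1,440, with no new visits or staff. The downsides are a few primary values made missing by a post-randomisation event, and a sensitive question. The analysis rule can wait until just before unblinding. The question should start before follow-up visits where possible, since status not recorded then may be lost.

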Secondary outcome measures. The secondary outcome measure will be the "Life's Simple 7" Composite Score, which is adapted from the American Heart Association standards based on health assessment data¹⁴⁶: average blood pressure from 3 readings, fasting lipid panel and glucose, height, weight, self-reported cigarette smoking status, dietary quality, and physical activity patterns). Point values are assigned to each component: 2 points for ideal, 1 point for intermediate, 0 points for poor. The total sum allows for a continuous measure of cardiovascular health ranging from poor to ideal (0-14 points). The final score will be categorized as 0-6 (poor), 7-8 (intermediate), 9-14 (ideal). In previous studies, adherence to the ideal Life's Simple 7 metrics was found to be associated with decreased risks of cardiovascular disease¹⁴⁷ and all-cause mortality¹⁴⁸.

Seated blood pressure (systolic and diastolic) measurements will be made on the right arm using an automated BP Tru BPM-200 after sitting quietly for five minutes.¹⁴⁹ Blood pressure will be measured three times and the average of the second and third readings will be used in analyses. Fasting glucose and cholesterol will be collected by a single finger prick obtained by Mayo Clinic CRU staff. Participants will be asked to refrain from eating for at least 6 hours prior to testing. The portable Whole Blood Lipid Screen Cholestech LDX Analyzer will

be used to analyze specimens, which combines enzymatic methodology and solid-phase technology measured by reflectance photometry to measure total cholesterol, HDL cholesterol, triglycerides and glucose in whole blood. LDL cholesterol is a calculated value. Samples used for testing are whole blood from a fingerstick collected in a lithium heparin coated capillary tube. Results will be recorded at the site of collection and samples will be destroyed upon recording of results.

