Dietary Quality: Two 24-hour dietary recalls will be collected using the Automated Self-administered 24-hour Recall (ASA24) system, a National Cancer Institute web-based tool that enables multiple automated self-administered 24-hour recalls. The recalls will be performed using a computer under the supervision of study staff. The tool is available in English and Spanish. A study staff member and an interpreter will complete the recall with participants who speak other languages. Through these intake estimates, the effect of the intervention on diet quality (Healthy Eating Index plus intake of fruits, vegetables, sweetened beverages, percent energy from fat and total calorie consumption) may be examined.

Physical activity: The International Physical Activity Questionnaire (IPAQ)¹⁵⁶ will be used to assess the number of minutes of mild, moderate, and vigorous physical activity over the previous 7 days. We have used objective measures of physical activity in past studies (accelerometers) as a primary outcome,⁴⁴ but for this study the survey will be used only to observe changes over time, not as an objective measure of activity.

Table 4. Life's Simple 7 domains and derivation of its composite score¹⁵⁷⁻¹⁵⁹

“Life’s Simple 7” Domain	Optimal (2 points)	Intermediate (1 point)	Poor (0 points)
Weight	BM<25	BMI 25-29.9	BMI ≥30
Blood pressure	SBP<120 and DBP<80	SBP 120-139 and DBP 80-89	SBP≥140 or DBP≥90
Total cholesterol	<200 mg/dL	200-239 mg/dL	≥240 mg/dL
Fasting glucose	<100 mg/dL	100-125 mg/dL	≥126 mg/dL
Smoking status	Never or quit >12 months ago	Former or quit ≤12 months ago	Current
Diet	HEI≥69.3	HEI 56.9-69.2	HEI<56.9
Physical activity	≥150 min/wk moderate or ≥75 min/wk vigorous or ≥150 min/wk moderate+vigorous	1-149 min/wk moderate or 1-74 min/wk vigorous or 1-149 min/wk moderate+vigorous	None
Composite Score	9-14	7-8	0-6

Health-related Quality of Life will be measured by single-item linear analog scale assessments of physical, emotional, and overall health developed by members of our research team^{160,161}.

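### The blood pressure row of Table 4 has no score for a participant with one pressure intermediate and the other optimal, so the Life's Simple 7 composite is undefined for an estimated quarter of participants

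*Combined protocol and SAP*

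**What the plan says.** The section Secondary outcome measures names the Life's Simple 7 composite as the secondary outcome and sets the scoring: "Point values are assigned to each component: 2 points for ideal, 1 point for intermediate, 0 points for poor". The seven scores are summed to 0-14.

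Table 4 gives these blood pressure cells:

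- 2 points: "SBP<120 and DBP<80"
- 1 point: "SBP 120-139 and DBP 80-89"
- 0 points: systolic 140 or above, or diastolic 90 or above

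No rule covers a systolic and a diastolic value that point to different cells. The only related provision is the missing-data paragraph in Data Analysis: "Simple imputation methods such as minimum, average, or maximum values carried forward will be followed by multiple imputation methods".

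Two smaller points lie in the same derivation. The composite's input list has "average blood pressure from 3 readings", while the next paragraph says "the average of the second and third readings will be used in analyses". In the smoking row, the 2-point cell is "Never or quit >12 months ago" and the 1-point cell is "Former or quit ≤12 months ago".

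**The concern.** A three-level score has to place every measured value in exactly one level. In the blood pressure row, optimal and intermediate are both joined by 'and', so discordant pairs fall between them. The imputation plan does not help: both pressures were measured, and only their category is undefined. The programmer would have to choose a rule, possibly after seeing data.

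The choice is not neutral between arms. The share in the gap changes as blood pressure falls, and the intervention is meant to lower it. Dropping these records, imputing them, or scoring them 0 or 1 gives different contrasts in the blood pressure component of the named secondary outcome.

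**Working it through.** **Logic.** No assumption is needed for the gap itself.

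| | DBP <80 | DBP 80-89 | DBP ≥90 |
|---|---|---|---|
| SBP <120 | 2 | no cell | 0 |
| SBP 120-139 | no cell | 1 | 0 |
| SBP ≥140 | 0 | 0 | 0 |

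The pilot's own week-12 mean, 127.2/75.8 (Table 2), lies in a square with no score.

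**Inputs.** The plan gives no figure for this, so there is none to reproduce. Table 2 of the pilot (N=39) gives mean (SD):

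- Baseline: SBP 133.9 (16.9), DBP 81.0 (9.5)
- Week 12: SBP 127.2 (15.8), DBP 75.8 (9.6)

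Bivariate normality and a correlation r of 0.4 to 0.8 are assumptions that are not in the documents.

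**Share in the gap.** P(gap) = P(120 ≤ SBP < 140, DBP < 80) + P(SBP < 120, 80 ≤ DBP < 90).

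| r | Baseline | Week 12 |
|---|---|---|
| 0.4 | 0.213 + 0.054 = 0.267 | 0.307 + 0.050 = 0.357 |
| 0.6 | 0.221 + 0.037 = 0.258 | 0.309 + 0.030 = 0.339 |
| 0.8 | 0.233 + 0.015 = 0.248 | 0.318 + 0.009 = 0.327 |

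Rounding averages to 0.5 mm Hg gives 0.273/0.264/0.253 at baseline and 0.361/0.344/0.332 at week 12. With r from 0 to 0.9 and either continuous or whole-unit cut points, the baseline share stays within about 24-28%. For the planned 378 participants, 0.248 × 378 = 94 and 0.267 × 378 = 101.

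At r = 0.6 the baseline cells are optimal 0.165, intermediate 0.172, poor 0.405 and gap 0.258. The gap is larger than the intermediate cell.

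**Effect of the programmer's choice.** For illustration, put the control arm at pilot baseline values and the intervention arm at week-12 values. Mean blood pressure points are:

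- gap scored 1: 2·P(optimal) + P(intermediate) + P(gap)
- gap dropped: [2·P(optimal) + P(intermediate)] / [1 − P(gap)]
- gap scored 0: 2·P(optimal) + P(intermediate)

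At r = 0.6:

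- gap scored 1: 1.060 − 0.760 = 0.299 (from unrounded means)
- gap dropped: 1.090 − 0.677 = 0.414 (from unrounded means)
- gap scored 0: 0.721 − 0.502 = 0.219

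| Handling | r=0.4 | r=0.6 | r=0.8 | Ratio to gap scored 1 |
|---|---|---|---|---|
| Gap scored 1 | 0.310 | 0.299 | 0.285 | 1 |
| Gap dropped | 0.428 | 0.414 | 0.394 | 1.38 |
| Gap scored 0 | 0.221 | 0.219 | 0.205 | 0.71-0.73 |

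**Would changing 'and' to 'or' be enough?** Not quite. A reading of 130/92 would then meet both the 1-point and the 0-point cell. Averages of two readings can also land on 139.5 or 89.5, between the whole-number bounds; in the 0.5 mm Hg simulation this leaves 0.3-0.6% unclassified. A residual definition leaves none.

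**Smaller points.** A former smoker who quit more than 12 months ago satisfies the 2-point smoking cell and also the word 'Former' in the 1-point cell. The three-reading and two-reading averages are different numbers whenever the first reading differs from the mean of the other two.

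**The case against.** The strongest reply is that this is a wording slip. On an ordered 2/1/0 scale with an 'and' rule at the top and an 'or' rule at the bottom, a pair that is neither optimal nor poor belongs in the middle, and most analysts would score it 1. Scoring it 0 contradicts the explicit poor cell, and nothing in the plan suggests discarding measured values. That is a fair reading of intent, but the plan does not state it.

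The size can also be challenged, and these qualifications stand:

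- **The illustration is generous.** It treats an uncontrolled pilot change as the treatment effect: 6.7/16.9 = 0.40 SD systolic and 5.2/9.5 = 0.55 SD diastolic. The sample size section assumes 0.1 SD change in controls and 0.4 SD in the intervention group for the primary endpoints. Applied to both pressures with baseline SDs, the gap holds 26-29% of controls and 28-33% of the intervention arm, an imbalance of 2-4 percentage points. The difference with the gap scored 1 is 0.20-0.21. Scoring the gap 0 then shrinks it by 11-20%, but dropping the records still inflates it by 37-40%.
- **The contrasts are in blood pressure points, not composite points.** In absolute terms the choice moves the illustrated difference by about 0.08-0.12 points. The relative effect on the seven-component sum was not computed.
- **The range 25-27% reflects only the unknown correlation.** Shifting each baseline mean by 1.96 standard errors (2.71 and 1.52 mm Hg at N=39) widens it to about 18-32%.
- **The averaging and smoking points are small.** The sentence on readings 2 and 3 is the operative analysis rule, and the 12-month cut in the 2-point smoking cell largely settles that overlap.

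**Conclusion.** The concern holds. The scoring rule fails when followed as written: two of the nine combinations of systolic and diastolic range have no score, and nothing else in the plan supplies one. That part rests on no assumption.

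The size is an estimate that depends on a 39-person pilot, normality and the assumed correlation. Even with the pilot's sampling error included, close to a fifth or more of participants would be affected at baseline values. Dropping the affected records inflates the blood pressure contrast by nearly two fifths in both scenarios examined; scoring them 0 shrinks it by 11-29%.

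The consequence is limited to the composite and its categories. The primary endpoints and separate analyses of systolic and diastolic pressure do not use this table, and the composite can be rescored from stored readings. It should be fixed, but it does not threaten the trial's main result.

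**What to change.** Define the 1-point blood pressure cell as everyone neither optimal nor poor: systolic at least 120 and below 140, or diastolic at least 80 and below 90, and not meeting the 0-point cell. This follows from the table's own outer cells, leaves nobody with measured pressures unclassified, and covers half-unit averages.

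Two minor edits belong with it:

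- State one averaging rule for the composite and the other blood pressure analyses. The analysis sentence already specifies readings 2 and 3.
- Reduce the 1-point smoking cell to those who quit 12 months ago or less, which matches the cut in the 2-point cell.

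The cost is three edits to the table or text before the scoring program is written and before outcome data are examined. No new data are needed.
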